Official Title of the Study: Transmitted Light Tissue Analysis (TiLTT) (TiLLT)

Document Date: January 15, 2015

NCT Number: NCT02749201

Transmitted Light Tissue Thickness Analysis (TiL/TT) (TiLLT)

The most common surgical procedure for weight loss is the sleeve gastrectomy. The laparoscopic sleeve gastrectomy (LSG) involves the linear stapling of the stomach using a stapling device [e.g. Echelon (Ethicon Somerset NJ)] fired multiple times along the length of the stomach thereby excising 80-90% of the stomach leaving the patient with a "sleeve" of stomach rather than the normal anatomical pouch. The gastric wall varies in thickness and thus there are a varied staple sizes available for this use. Staple sizes range from 2.0mm-5.0mm in height. In standard surgical practice the surgeon chooses the size of staple cartridge for each subsequent firing based on his experience and estimations about the thickness of the stomach tissue in any given region. The drawback of this technique is that it is highly inaccurate. If the surgeon's estimation is in error, the staple height chosen may be either too tall or too short leading to bleeding or leakage from between the staples or malformed/unformed staples leading to staple line failure. Any of these errors can lead to devastating complications such as hemorrhage, leak, sepsis and death. To date there is no objective way to measure the thickness of the tissue being stapled and thus staple choice relies entirely on surgeon estimation which is inherently inaccurate. We hypothesize that a light source placed in the stomach lumen will transmit light through the gastric wall. The amount of light transmitted, i.e. visible to an imaging device arrayed external to the stomach, will be directly proportionate to the thickness of the stomach. This study will take advantage of the fact that during routine procedures in the sleeve gastrectomy procedure a lighted tube is placed into the gastric lumen via the mouth. This device is called the Gastrisail and has 10 separate LED lights arrayed along its length. This allows for the measurement of transmitted light intensity through the gastric wall at 10 individual locations along the length of the stomach. In addition this study will take advantage of the fact that during standard practice in a sleeve gastrectomy a section of the stomach corresponding to the location of the lights is excised and sent for pathological evaluation. This will allow us to measure the actual thickness of the stomach at 10 points corresponding to the locations of the transmitted light intensity. For this measurement we will use a standardized and validated measurement tool/calipers. Now with two sets of numbers we plan to correlate the degree of transmitted light intensity with actual thickness measurements and thereby reach an algorithm which will allow the transmitted light intensity data alone to predict gastric wall thickness. This will provide the surgeon with an entirely non-invasive objective measure of gastric wall thickness and hopefully improve his/her choice of staple size during these surgical procedures thus improving safety.

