
The aim of this project is to create a noninvasive method of predicting the thickness of the gastric wall. This information can then be used to aid the surgeon in picking the correct size staple cartridge when stapling the stomach during sleeve gastrectomy surgeries.

Methods: We propose to use a standard gastric sizing bougie (plastic guide placed into the stomach at the time of stapling designed to help outline a standardized staple line) used in

common surgical practice (Gastrisail, Covidien). This bougie comes with 10 LED lights arrayed along its length. The wavelength and light intensity of these LED's is standardized. The bougie is routinely placed via the mouth, down the esophagus and into the distal stomach. the bougie will be retained in place throughout the stapling process as per standard technique. The use of the bougie is part of the standard procedure of sleeve gastrectomy and is used in 100% of all sleeve operations.

Using a standard high definition laparoscope, images of these lights within the gastric lumen will be captured. The images will then be uploaded and processed using a software package provided by ImageIQ, Inc. The software will measure the light intensity at each of the 10 LED positions on the bougie, thereby obtaining 10 individual intensity readings at 10 different sites along the length of the stomach.

There will be no measurements made on the in-vivo stomach but simply an image made of the stomach with the lighted bougie in-situ. The analysis of the light intensity from the image and data extraction will be done after the completion of the surgery using software provided by the ImageIQ corporation.

The stomach will be stapled as per standard surgical routine and the specimen side of the gastric body will be separated from the remnant stomach and removed from the abdominal cavity as per standard surgical practice. Prior to this specimen being sent to the pathology department, on the back table, a standardized, validated thickness measuring tool will be used to measure the thickness of the gastric specimen ex-vivo at the identical 10 points as light intensity imaged at the LED's.

A mathematical formula will then be created to correlate the data obtained by light transmittance through the gastric wall and the mechanical measurements of the gastric specimen we obtained using a scientific calipers. The formula will be derived as a directly proportional calculation with where $y=kx$ and k is a non-zero constant.

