This predictive algorithm will allow non-invasive gastric wall thickness measurements in real-time based solely on imaged light transmittance using nothing more than a standard lighted bougie and standard laparoscope.

The study will be conducted in the operating room and will have two halves of data collection. Firstly there will be images taken intraoperatively of the lighted bougie while in proper position within the gastric lumen. Secondly there will be gastric wall thickness measurements taken of the explanted stomach specimen on a back table in the operating room prior to it being sent to the pathology department. This data collection will yield 20 measurements per patient (10 from each of these two sources). Thus each patient will be enrolled in the study only intraoperatively. Following collection of the data for all included patients (see below statistical methodology) the data from each of these sources will be analyzed and the predictive algorithm constructed.

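### The plan fits one constant k and asserts that light then measures thickness, but the text states no prediction error in mm, no comparator and no patient-level uncertainty

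*Combined protocol and SAP*

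**What the plan says.** The Methods paragraph on image processing describes "obtaining 10 individual intensity readings at 10 different sites along the length of the stomach", with a caliper reading of the excised specimen at each matching site. The closing paragraph on study conduct gives the count: "This data collection will yield 20 measurements per patient (10 from each of these two sources". That makes 10 pairs per patient.

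The Methods paragraph on the formula sets the model: "The formula will be derived as a directly proportional calculation", y = kx, where "k is a non-zero constant". The next paragraph states what follows from it: "This predictive algorithm will allow non-invasive gastric wall thickness measurements in real-time based solely on imaged light transmittance". The opening background paragraph also says "we plan to correlate the degree of transmitted light intensity with actual thickness measurements".

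On analysis, the closing paragraph says only this: "Following collection of the data for all included patients (see below statistical methodology"), after which "the data from each of these sources will be analyzed and the predictive algorithm constructed". The section it points to does not appear in the document. The text gives no number of patients, accuracy criterion, interval, comparator or patient effect.

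**The concern.** The aim is prediction: a surgeon is eventually to read wall thickness from an image. The evidence for that is how far the prediction misses in a patient who did not contribute to k, and whether the miss is smaller than it would be without light. The text states neither.

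Deriving k does not fill the gap. With positive light and positive thickness, a least-squares line through the origin always has a positive slope, whether thickness rises with light, falls with it or is unrelated to it. The step that produces the algorithm therefore cannot fail, and a non-zero k is not evidence for the hypothesis. A through-origin fit can also look good on its own scale while predicting worse than a constant.

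What is at stake is the conclusion the study can draw, not the care of its participants. Images are analysed after surgery and stapling follows usual practice.

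**Working it through.** **The plan's own figure.** 10 sites × 2 sources = 20 measurements, or 10 pairs, per patient. This reproduces. The text gives no sample size, power or precision figure to check.

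**Assumptions.** The plan does not define x and y or name the fitting method. I take x as light, y as thickness, and least squares through the origin. The documents give no mean thickness and no coefficient of variation (CV), so I assume CV 0.3 for thickness, CV 0.1 to 0.5 for light, and a mean thickness of 2 or 3 mm. The test case is light that carries no information about thickness.

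**Sign of k.** k = Σxy / Σx². Every term is positive, so k > 0 for any positive data.

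**Error of y = kx when light is uninformative.** In large samples, with m the mean thickness:

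- RMSE / m = √[(1 + CVy²) − 1/(1 + CVx²)]
- RMSE / m for predicting the mean = CVy
- uncentred R² = 1 / [(1 + CVx²)(1 + CVy²)]

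At CV 0.3 each:

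- y = kx: √(1.09 − 1/1.09) = √0.1726 = 0.415
- mean only: 0.300
- ratio: 0.415 / 0.300 = 1.38
- uncentred R²: 1 / (1.09 × 1.09) = 0.84

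In mm this is 0.83 against 0.60 at mean 2 mm, and 1.25 against 0.90 at mean 3 mm.

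| Light CV | RMSE/m, y = kx | RMSE/m, mean only | Excess |
|---|---|---|---|
| 0.1 | 0.316 | 0.300 | 5% |
| 0.2 | 0.358 | 0.300 | 19% |
| 0.3 | 0.415 | 0.300 | 38% |
| 0.5 | 0.539 | 0.300 | 80% |

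The choice of least squares does not drive this. Taking k as the ratio of means gives √(0.3² + 0.3²) = 0.424, which is 41% above 0.300.

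**Which missing element does the 38% measure?** Simulation with 20 patients, 10 sites, mean 2 mm, CV 0.3 each, 1,500 runs:

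| Error | y = kx | Mean only | Ratio |
|---|---|---|---|
| In-sample | 0.826 mm | 0.598 mm | 1.38 |
| Each whole patient left out | 0.830 mm | 0.600 mm | 1.38 |

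The ratio is the same, and it is also 1.38 in-sample with 10 and 50 patients. k was positive, and in-sample error was worse than the mean, in every run. The excess is what a missing comparator would hide. It is not the cost of a missing out-of-patient check.

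**What leaving patients out adds.** It matters when k differs between patients. Assume a between-patient CV of 20% for k, light uniform from 1.5 to 4.5, and residual SD 0.3. In-sample against left-out RMSE is then 0.666 against 0.729 with 10 patients (9% more), 0.680 against 0.710 with 20 (4%), and 0.687 against 0.699 with 50 (2%). The gain is modest, but left-out error is the quantity that describes a new patient.

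**What the planned correlation adds.** In the uninformative case with 20 patients, the middle 95% of correlations ran from about −0.13 to 0.14. It would expose absent association. It would not give an error in mm.

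**The case against.** The strongest reply is that the closing paragraph cites a statistical section that is not in the document, and that validation, clustering and sample size would normally sit there. This stands. The point is limited to the text as it is, and nobody can say that the investigators will omit these analyses.

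A second reply is that the planned correlation already guards against a useless formula. This stands in part: a correlation near zero would be visible. But no consequence is attached to it, and a correlation well above zero still would not say how many millimetres the prediction misses by.

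Three stronger readings are tempting and are not supported.

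- A reader might infer that the plan pools pairs as independent and so overstates the precision of k. The text proposes no interval for k and does not say how pairs are treated. If such an interval were computed, its error would have no fixed direction. With no position effect, positive within-patient correlation makes it too narrow: coverage is about 85% at an assumed intraclass correlation of 0.1. A shared position effect unrelated to light, with SD equal to the residual SD, brings coverage to about 96% at the same correlation.
- A reader might infer that only error in left-out patients could expose an uninformative formula. The simulation shows that in-sample error beside the mean exposes it equally well.
- A reader might infer that the study would necessarily present a worthless predictor as valid. With a correlation planned and a statistical section cited, the documents do not support that.

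**Conclusion.** The point holds for the text as it is. The plan moves from fitting k to asserting measurement from light alone without stating a prediction error in mm, a comparator or patient-level uncertainty. Since k is positive for any positive data, deriving it is not evidence of prediction.

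The illustrative size is 38% more error than predicting the mean (0.83 against 0.60 mm at mean 2 mm), and 5% to 80% over light CV 0.1 to 0.5. These figures describe uninformative light under assumed CVs and means; they do not forecast this study's result. They should be cited as the cost of having no comparator, not of having no out-of-patient check. This should be corrected before analysis. Confidence is medium because the cited statistical section could resolve it.

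**What to change.** First supply the cited statistical section. If it already covers the items below, nothing needs to change. Otherwise add:

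1. **Prediction error.** Refit k with each whole patient left out, predict that patient's 10 sites, and report the error of y = kx in mm.
2. **Comparator.** Report beside it the same left-out error for a mean-only prediction and, as a secondary comparator, for an LED-position-only prediction. Claim prediction only if light improves on the comparator.
3. **Inference, if any is reported.** Make the patient the unit for any interval or test on k or on the correlation. For k, use patient-clustered standard errors with a t reference on patients minus 1 degrees of freedom. In simulation this covered 0.946 to 0.955 with 5, 10 and 20 patients. A percentile bootstrap over patients covered only about 0.82 to 0.84 with 5 patients and about 0.89 to 0.92 with 10, so it is not a safe substitute when patients are few.

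The cost is analysis wording and a little extra computation on data already planned. Patient and LED number must be kept with each pair. The price is that intervals may be wider.
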